5.5.2. Patient Disposition

The number and percentage of ITT patients who complete the study or discontinue early will be tabulated for all treatment groups for SP III and SP IV separately. Reasons for discontinuation will be compared between treatment groups using Fisher's exact test for SP III. Descriptive statistics only will be presented for the treatment groups in SP IV. In addition, subcategories of discontinuation due to subject decision will be summarized.

Patient allocation by investigator will be summarized for SP III for all ITT patients. Patient allocation by investigator will also be listed for all study periods.

5.5.3. Important Protocol Deviations

Important protocol deviations that potentially compromise data integrity or patients' rights or safety will be summarized by treatment group for the ITT population for SP II/III and for the open-label treatment population for SP IV.

Section 7 (appendix) lists the categories, subcategories, and study-specific terms of important protocol deviations, source of identification, and the method to identify each deviation. Per study team's discretion, for non-programmable protocol deviations, additional categories and subcategories other than the ones in Section 7 (appendix) can always be added to the final non-programmable protocol deviations list as deemed necessary.

Tables and listings of important protocol deviations for ITT population during all study phases will be provided by randomized treatment group.

5.5.4. Patient Characteristics

The following patient characteristics at baseline will be summarized by treatment group.

- Demographic (age, sex, ethnic origin, height, weight, BMI)
- Migraine and/or headache measures per 30-day baseline period:
 - o number of migraine headache days
 - o number of ICHD migraine headache days
 - o number of headache days
 - o number of migraine headache hours
 - number of headache hours
 - o number of migraine attacks
 - o number of monthly days with abortive medication use
 - o number of migraine headache days with nausea and/or vomiting
 - o number of migraine headache days with photophobia and phonophobia

- o number of migraine headache days with aura
- o number of migraine headache days with prodromal symptoms other than aura
- Number of prior migraine preventive medication categories failed in the past 10 years: 2, 3, or 4
- Patient Global Impression Severity
- Alcohol, tobacco, caffeine, and nicotine consumption
- Medical history and preexisting conditions
- Presence of aura at baseline
- CCI
- CC
- Contraindications to migraine preventive medications

Comparisons between treatment groups will be performed using Fisher's exact test for categorical data and ANOVA with treatment as independent variable in the model for continuous data.

Medical history and preexisting conditions will be summarized by descending frequency of preferred term (PT) within system organ class (SOC), and comparison between treatment groups will be performed using Fisher's exact test. Medical history is defined as illness(es) that ended prior to the signing of informed consent. Preexisting conditions and AEs at baseline are those AEs occurring during the baseline/screening visits for the study period, that is, Visit 1, Visit 2, and Visit 3.

5.5.5. Exposure to Investigational Medicinal Product

Patients will receive the investigational medicinal product (IMP) at the following planned time points:

- Beginning of Month 1 (Visit 3)
- Beginning of each month from Month 2 to Month 6 (Visit 4 to Visit 9)

The following information will be recorded on the eCRF for each dose:

- Confirmation that the patient received the IMP (including reason if the IMP was not given)
- Date and time of administration

The following will be derived from the information recorded on the eCRF:

• For SP III, duration of exposure in days is calculated as double-blind treatment phase disposition date – first date IMP administered +1.

- For SP IV, duration of exposure in days is calculated as open-label disposition date first date IMP administered during SP IV +1.
- For SP III and SP IV separately, number and percentage of patients with 1 dose, 2 doses, and 3 doses injected.

Comparisons between treatments using the safety population for duration of IMP exposure will be performed using an ANOVA with treatment, baseline migraine frequency category, and pooled country in the model. The number of patients with 1 dose, 2 doses, and 3 doses will be summarized and treatment groups will be compared using Fisher's exact test. The number of patients with 1 dose, 2 doses, 3 doses, 4 doses, 5 doses, and 6 doses injected will be summarized for the GMB-treated population. In addition, injections not administered with the corresponding reasons will be listed.

Information about the use of comfort measures before or after the injection will be collected. The use of comfort measures will be summarized.

5.5.6. Treatment Compliance

Treatment compliance will be calculated for each treatment period (SP III and SP IV separately) as:

number of doses received * 100 number of intended doses

For this analysis, partial dose (for example, a patient only received 1 injection instead of 2 at Visit 3 or Visit 6) will be considered as no dose received.

For SP III, comparisons between treatments in the ITT population for treatment compliance will be performed using an ANOVA with treatment, baseline migraine frequency category, and pooled country in the model.

Treatment compliance for SP IV will be summarized similarly.

5.5.7. Electronic Patient-Reported Outcomes Diary Compliance

Electronic patient-reported outcomes diary compliance at each 1-month period (including baseline, Month 1, Month 2, ... to Month 6) as well as for SP III overall (Month 1 through Month 3) will be calculated. Diary compliance at each 1-month period is calculated as:

 $\frac{\text{Actual number of diary days in the period}}{\text{Expected number of diary days in the period}}*100$

Expected number of ePRO diary days is calculated as date of injection at the end of the interval minus date of injection at the beginning of the interval +1.

For a patient who discontinues early in the double-blind (SP III) or open-label treatment phase (SP IV), compliance rate for the last month of that patient will be calculated with a denominator of 30 days (or the actual number of days in the interval if it is greater than 30).

Treatment comparisons for ePRO diary compliance for SP III will be performed using an ANOVA with treatment, baseline migraine frequency category, and pooled country in the model. ePRO diary compliance for SP IV will be summarized.

5.5.8. Previous Migraine Prevention Therapy

Prior Therapy: Migraine Preventives Lifetime

The proportion of patients with response to the previous migraine prevention therapy within each of the 6 categories (to enter this trial, medical history event, adequate response, inadequate response, no response, and treatment availability) will be summarized by medication. Treatment group comparisons will be done using Fisher's exact test. Previous migraine prevention therapies are those therapies that started prior to the date of the first injection and stopped prior to or on the date of first injection and the indication is "primary study condition."

Reasons for Discontinuation of Previous Migraine Prevention Therapy will be summarized by medication. If a patient discontinued the same medication multiple times with different reasons, the most recent reason will be included in the summary table.

The total number of medications that patients failed lifetime (derived from CRFs for both lifetime and past 10 years) will be calculated for each patient and will be summarized.

Prior Therapy: Failures during Past 10 Years

The proportion of patients who previously failed migraine prevention therapy (i.e., who discontinued the therapy due to "medical history event," "inadequate response," or "no response") in the past 10 years will be summarized by medication category. Treatment group comparisons will be done using Fisher's exact test. The reasons for failures will be summarized by medication within each medication category. If a patient failed the same medication multiple times with different reasons, the most recent reason will be included in the summary table.

The total number of medications that patients failed in the past 10 years that meet protocol inclusion criterion #4 (derived from the CRF for the past 10 years) and the total number of medications that patients failed in the past 10 years, including medications that do not meet inclusion criterion #4 (derived from the CRF for the past 10 years and the CRF for lifetime with an end date within past 10 years) will be calculated for each patient and will be summarized.

5.5.9. Concomitant Therapy

The proportion of patients who received concomitant medication recorded on the general concomitant eCRF will be summarized for the ITT population for SP III and SP IV separately, as will the proportion of patients who took abortive medications as recorded on the patient acute headache medication log, which will also be summarized separately for SP III and SP IV. Concomitant therapies for SP III are those that were stopped during SP III or continued in SP III. If a medication was started and stopped on the same day as the first injection, it will still be considered a concomitant medication for SP III. If a medication was started before the first day of injection but was stopped on the same day of injection, it will not be counted as concomitant

medication for SP III. Concomitant therapies for SP IV are those that were started, stopped, or continued in SP IV.

Treatment group comparisons will be done using Fisher's exact test for Study Period III. Only descriptive statistics will be presented for the treatment groups in Study Period IV.

5.5.10. Efficacy Analyses

5.5.10.1. Primary Outcome and Methodology

The primary objective of this study is to test the hypothesis that galcanezumab (120 mg per month with a 240-mg loading dose) is superior to placebo in the prevention of migraine headache in treatment-resistant migraine patients.

The primary analysis will evaluate the efficacy of galcanezumab compared with placebo on the overall mean change from baseline in the number of monthly migraine headache days during the 3-month double-blind treatment phase.

The primary analyses will be performed using a REML-based MMRM technique. The analysis will include the fixed categorical effects of treatment, pooled country, month, and treatment-by-month interaction, as well as the continuous fixed covariates of baseline number of migraine headache days and baseline-by-month interaction.

An unstructured covariance structure will be used to model the within-patient errors. The Kenward-Roger (Kenward and Roger 1997) approximation will be used to estimate the denominator degrees of freedom. If the model does not converge with both the Hessian and the G matrix being positive definite under the default fitting algorithm used by PROC MIXED, the Fisher scoring algorithm will be implemented by specifying the SCORING option in SAS. If the model still fails to converge, the model will be fit using covariance matrices of the following order specified by a decreasing number of covariance parameters until convergence is met:

- Heterogeneous Toeplitz
- Heterogeneous First-order autoregressive
- Toeplitz
- First-order autoregressive

When the unstructured covariance matrix is not utilized, the sandwich estimator (Diggle and Kenward 1994) will be used to estimate the standard errors of the fixed effects parameters. The sandwich estimator is implemented by specifying the EMPIRICAL option in SAS®. When the sandwich estimator is utilized, the Kenward-Roger approximation for denominator degrees of freedom cannot be used. Instead, the denominator degrees of freedom will be partitioned into between-subject and within-subject portions by the DDFM=BETWITHIN option in SAS®. SAS® PROC MIXED will be used to perform the analysis.

The primary endpoint of this study for galcanezumab compared with placebo will be estimated as the treatment main effect from the MMRM analysis model. This provides the average treatment effect across Month 1, Month 2, and Month 3. The Type I error rate for the study will

be controlled at a 2-sided 0.05 level (equivalently, 1-sided 0.025 level). Specific details of the testing procedure for the primary outcome and the secondary gatekeeper objectives are provided in Section 5.5.10.4.

The results of the statistical tests at each month in the double-blinded treatment phase will be used to assess the onset of effect for galcanezumab compared with placebo. In particular, if the primary efficacy analysis is statistically significant, then the earliest month where the statistically significant improvement is observed and maintained for all the subsequent months during the double-blinded treatment phase will be considered as the period that demonstrated the onset of effect. If the onset of effect occurs in Month 1, the number of weekly migraine headache days in Month 1 will be analyzed to identify the earliest week where the statistically significant improvement is observed and maintained for all the subsequent weeks in Month 1. Details about the analysis for the number of weekly migraine headache days are described in Section 5.5.10.3.

5.5.10.2. Sensitivity Analysis for Primary Outcome

Two types of sensitivity analyses are planned to assess the robustness of deviations from the assumptions of primary analysis including normality assumption and missing data assumption.

Missing Data Assumption

Sensitivity analyses will be performed to assess the robustness of the primary analysis conclusions to deviations from missing at random (MAR) assumption. The approach for these analyses is to vary the assumptions of missing data for the primary analysis in a systematic way. Basically, the method will predict the missing outcomes and then add values (Δ_{120} , Δ_P) to the predictions in the galcanezumab and placebo treatment groups respectively, regardless of the reason the data are missing. This approach is consistent with the sensitivity approach suggested in Permutt (2015). This procedure will be repeated multiple times for different values of (Δ_{120} , Δ_P) using the following steps:

- 1) Predict the missing outcomes for each treatment via multiple imputation based on observed primary endpoint and baseline values. Such imputation will be carried out using a Markov Chain Monte Carlo method with a Jeffreys prior via SAS® PROC MI. Thirty (30) such imputations will be created.
- 2) Add the corresponding Δ value (that is, Δ_{120} , Δ_P) to the imputed values based on the patient treatment group.
- 3) Conduct the primary analysis separately for each of the 30 imputations.
- 4) Combine the results of these analyses using Rubin's combining rules, as implemented in SAS® PROC MI ANALYZE.

The above steps will be repeated multiple times for different values of (Δ_{120}, Δ_P) with Δ_P ranging from 0 to twice the absolute value of the mean value seen for placebo in the primary analysis, Δ_{120} ranging from Δ^P to Δ_P + absolute value of the biggest mean treatment difference seen within the primary analysis. For example, if the overall mean change from baseline for placebo is -3.6 and the maximum overall treatment difference is -1.5, then Δ_P would range from 0 to 7.2 and Δ_{120} would range from Δ_P to Δ_P + 1.5.

Normality Assumption

To assess the robustness of the MMRM results to deviations from normality assumption, a sensitivity analysis for raw number of migraine headache days (total number of migraine headache days for each interval without normalization to 30-day period) will be conducted with a repeated measures negative binomial regression model fitted with SAS PROC GLIMMIX. The model will include treatment, pooled country, month, and treatment-by-month interaction, as well as the continuous fixed covariates of baseline number of monthly migraine headache days and baseline-by-month interaction, log (number of compliant days within each month/30) as the offset in the model. In case of non-convergence, pooled country and/or baseline-by-month interaction may be excluded from the model. Directional consistency of treatment effects from this model and the primary analysis MMRM model as specified in Section 5.5.10.1 will be examined.

In addition, as another form of sensitivity analysis, residuals from the primary analysis MMRM model will be examined and outliers identified. Consistency of results before and after removing patients with outlier residuals will be examined.

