10.3. Statistical Analyses

10.3.1. General Statistical Considerations

Statistical analysis of this study will be the responsibility of Lilly or its designee. Details of statistical analysis methods will be described in the statistical analysis plan (SAP).

Unless otherwise specified, analyses will be conducted on the ITT population for efficacy analyses and on the safety population for safety analyses (see Section 10.2). When change from

baseline is assessed, the patient will be included in the analysis only if he/she has a baseline and a postbaseline measurement.

Continuous efficacy variables with repeated measures will be analyzed using mixed model repeated measures (MMRM) methods. The MMRM will include the fixed categorical effects of treatment, baseline migraine headache day frequency category (low episodic migraine, high episodic migraine, chronic migraine), pooled country, month, and treatment-by-month interaction, as well as the continuous fixed covariates of baseline and baseline-by-month interaction. For the model of the primary endpoint, the baseline migraine headache day frequency category will be excluded from the covariates since the continuous baseline monthly migraine headache day value is already in the model.

For continuous efficacy variables without repeated measures, an analysis of covariance (ANCOVA) model with last observation carried forward (LOCF) imputation will be used, which contains the main effects of treatment, baseline migraine headache day frequency category, and pooled country, as well as the continuous fixed covariate of baseline. Type III sum-of-squares for the Least Squares Means (LSMeans) will be used for the statistical comparisons.

Binary efficacy variables with repeated measures will be analyzed using a generalized linear mixed model (GLIMMIX) as pseudo-likelihood-based mixed effects repeated measures analysis. The GLIMMIX model will include the fixed, categorical effects of treatment, month, and treatment-by-month interaction, as well as the continuous, fixed covariate of baseline value.

For binary efficacy variables without repeated measures, comparisons between treatment groups will be performed using logistic regressions with the same model terms as the ANCOVA model. Pooled country may be removed to ensure model convergence.

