5.2. Determination of Sample Size

The study will enroll approximately 420 patients. Eligible patients will be randomized in a blinded fashion in a 1:1 ratio to placebo or galcanezumab (120 mg with a loading dose of 240 mg). With the assumption of a 10% discontinuation rate and an effect size of 0.39, it is estimated that this sample size will provide approximately 96% power that galcanezumab will separate from placebo at a 2-sided significance level of 0.05 for the intent-to-treat (ITT) population in this study.

The study is also powered for the subpopulation of patients with episodic migraine. The study will seek to enroll approximately 250 patients with episodic migraine as determined during the prospective baseline period (approximately 60% of the total population). With the assumption of a 10% discontinuation rate and an effect size of 0.46, it is estimated that this will provide

approximately 93% power that galcanezumab will separate from placebo at a 2-sided significance level of 0.05 for the episodic migraine sub-population in this study.

Assumptions in this sample size calculation were based on data from 3 double-blind, placebo-controlled, phase 3 studies, with an adjustment made to reflect differences in this study and the potential impact of the development phase and the inclusion of an open-label treatment phase on placebo responses.

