5.5.1.5. Baseline and Postbaseline Definition

Table CGAW.5.4 describes the rules for determining the patient population and baseline and postbaseline observations for each study phase and type of analysis. When "last of Visit x-x" is used in the table, the last non-missing observation obtained in the visit interval will be used.

Table CGAW.5.4. Patient Population with Baseline and Postbaseline Definitions by Study Period and Type of Analysis

Study Period/Analysis	Patient Population	Baseline Observation	Postbaseline Observation(s)		
Study Period III					
Efficacy analyses (Repeated measures) or average of observed monthly values		Visit 3	All scheduled visits 3 < Visits ≤6		
Efficacy analyses at LOCF endpoint	ITT population and ITT episodic sub-population	Visit 3	Last of Visit 3.01–6		
Health outcome analyses (Repeated measures)	with a baseline and at least 1 postbaseline observation	Visit 3	All scheduled visits 3 < Visits ≤6		
Health outcome analyses at LOCF endpoint or for average of observed monthly values		Visit 3	Last of Visit 3.01-6		
Treatment-emergent adverse events	Safety population	All Visits 1–3*a	All Visits 3.01–6		
Serious adverse events, discontinuations due to adverse events	Safety population	NA	All Visits 3.01–6		
Treatment-emergent abnormal laboratory values	Safety population with normal (with respect to direction being analyzed) laboratory values at all non-missing baseline visits and who have at least 1 postbaseline observation	Low: Min of Visits 1–3 High: Max of Visits 1–3 Abnormal: All Visits 1–3	Low: Min of Visits 3.01–6 High: Max of Visits 3.01–6 Abnormal: All Visits 3.01–6		
Treatment-emergent changes in temperature and weight	Safety population with a baseline and at least 1 postbaseline observation	Low: Min of Visits 1–3 High: Max of Visits 1–3	Low: Min of Visits 3.01–6 High: Max of Visits 3.01–6		
Treatment-emergent changes in blood pressures, pulse, and ECGs	Safety population with a baseline and at least 1 postbaseline observation	Low: Last of Visits 1–3 High: Last of Visits 1–3	Low: Min of Visits 3.01–6 High: Max of Visits 3.01–6		
Continuous safety analyses (Repeated Measures)	Safety population with a baseline and at least 1 postbaseline observation	Last of Visits 1–3	All scheduled visits 3 < Visits ≤6		
Continuous safety analyses – change from baseline to LOCF endpoint (ANCOVA)	Safety population with a baseline and at least 1 postbaseline observation	Last of Visits 1–3	Last of Visits 3.01–6		

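### The delta-adjusted sensitivity analysis in SAP 5.5.10.2 names no analysis set; under the SAP's general rule, dosed patients with no usable post-baseline month get no imputed value and no delta

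*SAP*

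**What the plan says.** **The sensitivity analysis (SAP 5.5.10.2).** Step 1 reads "Predict the missing outcomes for each treatment via multiple imputation based on observed primary endpoint and baseline values". Thirty imputations are made by MCMC. A delta is then added to the imputed values in each arm, whatever the reason for the missing data, the primary analysis is run on each completed set, and the results are pooled. The section names no population.

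**The inclusion rule (elsewhere).** Protocol 10.3.1 says that, when change from baseline is assessed, "the patient will be included in the analysis only if he/she has a baseline and a postbaseline measurement". SAP Table CGAW.5.4 (Section 5.5.1.5) defines the population for Study Period III efficacy analyses as ITT and ITT-episodic patients "with a baseline and at least 1 postbaseline observation". SAP 5.5.1.4 requires only randomization and one dose for ITT, and makes ITT the default unless the SAP states otherwise.

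**When a month is missing.** SAP 5.4.1 sets a month's diary endpoints to missing when compliance is 50% or less. For a patient who discontinues early, SAP 5.5.7 says the "compliance rate for the last month of that patient will be calculated with a denominator of 30 days", or the actual interval if that is longer.

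**The concern.** The purpose of the delta analysis is to show whether the primary conclusion survives departures from missing at random. A patient with no observed month contributes nothing to the primary MMRM, and would carry the delta in all three months if imputed. Leaving such patients out of the stress test as well means that an imbalance between arms in very early loss cannot move its result. Early loss may be related to outcome: under Protocol 8.2, a patient who requires a disallowed treatment shown to be effective for migraine prevention is discontinued before it is introduced.

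There is also a practical problem. Because 5.5.10.2 is silent on its population, two programmers could build different analysis sets, and the choice could be made after unblinding.

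**Working it through.** **Inputs.** SAP 5.2: "The study will enroll approximately 420 patients", 1:1 allocation (210 per arm), "With the assumption of a 10% discontinuation rate and an effect size of 0.39". SAP 5.5.10.2, example only: placebo mean change of -3.6 and a largest treatment difference of -1.5. These give a placebo delta from 0 to 7.2 and a galcanezumab delta from the placebo delta to 1.5 above it. The largest pair is 8.7 (galcanezumab) and 7.2 (placebo).

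**The plan's own figure.** With 0.9 × 210 = 189 per arm and a standardised effect of 0.39, power = Φ(0.39 × √(189/2) − 1.96) = Φ(1.83) = 96.7%, against "approximately 96% power that galcanezumab will separate from placebo at a 2-sided significance level of 0.05". The figure reproduces. It supplies the sample size and dropout rate used below, and the concern does not change it.

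**Who has no post-baseline value.** 15/30 = 50%, which is not above the threshold, so a patient who leaves with 15 or fewer diary days has Month 1 set to missing and has no later months. A patient who stays but has compliance of 50% or less in all three months is in the same position.

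**How many.** The documents do not say. Assumption: 10% discontinuation (42 patients), exits even over 90 days, complete diaries until exit.
- No usable month: 42 × 15/90 = 7 patients; 7/420 = 1.7%.
- Missing patient-months by day of exit: to day 15, 7 × 3 = 21; days 15 to 45, 14 × 2 = 28; days 45 to 75, 14 × 1 = 14; days 75 to 90, 7 × 0 = 0. The total is 63.
- The general rule removes 21 of these 63, one third of the values the delta would otherwise reach.

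**Size of the omitted shift.** Such a patient would carry the delta in all three months. So the shift in the treatment difference toward the null = (share of galcanezumab arm × galcanezumab delta) − (share of placebo arm × placebo delta). For 7 patients at 8.7 and 7.2:

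| Split, galcanezumab : placebo | Shares | Shift (days) | Share of 1.5 days |
|---|---|---|---|
| Equal (3.5 and 3.5) | 1.667%, 1.667% | 0.145 − 0.120 = 0.025 | 1.7% |
| 2:1 (4.67 and 2.33) | 2.222%, 1.111% | 0.193 − 0.080 = 0.11 | 8% |
| 5:1 (5.83 and 1.17) | 2.778%, 0.556% | 0.242 − 0.040 = 0.20 | 13% |
| 1:2 (2.33 and 4.67) | 1.111%, 2.222% | 0.097 − 0.160 = −0.06 | away from the null |

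**Other amounts of early loss.** With equal shares and a galcanezumab delta 1.5 above placebo, the shift is 1.5 × share: 0.015 day at 1%, 0.03 at 2%, 0.075 at 5%, and 0.15 at 10% (all 42 planned dropouts).

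**The case against.** **The case for no defect.** Section 5.5.10.2 contains no restriction. ITT is the default set, the delta applies whatever the reason for missingness, and baseline is a listed predictor, so MCMC can fill Months 1 to 3 from baseline alone. Imputation also comes before the primary model is run. In a completed dataset these patients do have post-baseline values, and Table CGAW.5.4 does not say whether an observation means observed or completed data.

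This stands as far as it goes: the exclusion is an inference from other sections. It does not settle the matter. The ITT default gives way where the SAP states otherwise, and Table CGAW.5.4 does so for Study Period III efficacy analyses. Nothing in 5.5.10.2 lifts that rule, and its third step points back to the primary analysis and so to the restricted set. Exclusion is the more natural reading.

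**The case that it hardly matters.** Under the even-exit assumption, 35 of the 42 dropouts are still in the analysis, and any month they are missing is delta-adjusted. Discontinuation reasons are compared between arms by Fisher's exact test (SAP 5.5.2) and adverse events leading to discontinuation are tabulated (SAP 5.5.12), so an imbalance would be visible. Protocol 3.3 reports few discontinuations due to adverse events in earlier studies. All of this is fair and keeps the point modest. But those tables do not show what the imbalance does to the primary comparison, which is the job of the sensitivity analysis.

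**Stronger readings that the documents do not support.**
- A reader might infer that only the earliest dropouts are affected. Patients who remain with poor diary compliance in every month are affected too.
- A reader might put the omitted shift at up to 0.36 day, 24% of the example effect (0.05 × 8.7 − 0.01 × 7.2 = 0.363). That needs 10.5 + 2.1 = 12.6 affected patients rather than 7, a 5:1 imbalance and the largest deltas together. A figure of 0.204 from 4% against 2% also needs 8.4 + 4.2 = 12.6. The documents give no reason to expect either.
- A reader might conclude that robustness is overstated or the primary result is in doubt. Neither is shown. The shift depends on an imbalance that has not been observed and could run the other way.

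**Conclusion.** The point holds in a limited form. SAP 5.5.10.2 leaves its analysis set unstated, and under Table CGAW.5.4 and Protocol 10.3.1 dosed ITT patients without a usable post-baseline month fall outside the delta-adjusted imputation. With balanced early loss the effect is negligible. At about 7 patients it becomes noticeable only if the loss runs clearly against galcanezumab and the largest deltas are used, and larger shifts need more early loss than the even-exit assumption gives. The count rests on that assumption and the sizes on the SAP's illustrative deltas; neither is a forecast. It is still worth correcting, because the rule weakens the analysis exactly where outcome information is absent, and the correction is nearly free.

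**What to change.** Add to SAP 5.5.10.2: 'As an exception to Table CGAW.5.4 and to the general baseline-and-postbaseline rule, the delta-adjusted multiple imputation includes all ITT patients with a baseline value, including those with no post-baseline month. All missing months (1 to 3) are imputed within treatment and the corresponding delta is added.' The exception must be explicit, or the new sentence would conflict with the table and with Protocol 10.3.1. Report the number of such patients in each arm. Leave the primary MMRM unchanged.

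Cost: one sentence, one added count and slightly more analysis work. Baseline is already an imputation predictor, so no substantial new programming is needed. SAP 5.5.1 allows changes of method that do not alter a principal feature of the protocol to be documented in the SAP or the clinical study report; the choice should be recorded before treatment assignments are known. The downside for the sponsor is that the sensitivity result may be less favourable.
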